6.3. Treatment Assessments (Weeks 2-96)

All study visits are to be scheduled relative to the Day 1 Visit date. Study visits are to be completed within \pm 2 days of the protocol-specific visit date through Week 12 and completed within \pm 6 days of the protocol-specific visit date through Week 36. The visit window at Week 48 will be \pm 6 weeks of the protocol-specific visit date, and this clinical visit window coincides with the Week 48 statistical analysis window for HIV-1 RNA. Unless notified by the Sponsor, Week 48 visit should be completed within \pm 6 days of the protocol-specific visit date. Following the Week 48 Visit, study visits are to be completed within \pm 6 days of the protocol-specific visit date through Week 84. The visit window at Week 96 will be \pm 6 weeks of the protocol-specific visit date. Unless notified by the Sponsor, Week 96 visit should be completed within \pm 6 days of the protocol-specific visit date.

The following evaluations are to be completed at the end of Weeks 2, 4, 8, 12, 24, 36, 48, 60, 72, 84, and 96, unless otherwise specified.

Note: Regularly scheduled evaluations will be made on all subjects whether or not they continue to receive study drug.

- Pre-dose (within 30 minutes prior to study drug administration) whole blood samples collection for plasma and PBMC samples (**Week 4 or Week 12 only**).

Note: Week 4 or Week 12 Visit should occur on the day of hemodialysis for this sample collection. Study drug administration should occur after completion of hemodialysis and should be observed on-site.

- PBMC sample processing will be performed by the central laboratory and plasma sample processing will be performed on-site. Details of the blood sampling procedures and sample management will be documented in the central laboratory manual.

- CCI
[REDACTED]
 - CCI
[REDACTED]
 - Review of AEs and changes in concomitant medications
 - Complete physical examination (**Weeks 24, 48, and 96 only**) (urogenital/anorectal exams will be performed at the discretion of the Investigator)
 - Symptom-directed physical examination as needed (**Weeks 2, 4, 8, 12, 36, 60, 72, and 84**)
 - Vital signs (blood pressure, pulse, respiration rate, and temperature) and weight
 - 12-lead ECG performed supine (**Weeks 48 and 96**)
 - Blood sample collection for the following laboratory analyses:
 - Chemistry profile: alkaline phosphatase, AST, ALT, GGT, total bilirubin, direct and indirect bilirubin, total protein, albumin, LDH, CPK, bicarbonate, BUN, calcium, chloride, creatinine, glucose, phosphorus, magnesium, potassium, sodium, uric acid, PT/INR, amylase (reflex lipase testing is performed in subjects with total amylase $> 1.5 \times \text{ULN}$) and PTH
- Note:** At Weeks 24, 48, 72, and 96, analyses of glucose will be done as part of the fasting metabolic assessments and not as part of the chemistry profile.
- Chemistry profile will include PT/INR only at Week 24 and Week 48
 - Sample should be drawn prior to hemodialysis
 - Timing of draw and timing of hemodialysis should be recorded
 - Metabolic assessments: Fasting (no food or drinks, except water, at least 8 hours prior to blood collection) glucose and lipid panel (total cholesterol, HDL, direct LDL, and triglycerides). If the subject has not fasted prior to the visit, the visit may proceed, but the subject must return within 72 hours in a fasted state to draw blood for the metabolic assessments (**Weeks 24, 48, 72, and 96 only**)
 - Estimated glomerular filtration rate according to the Cockcroft-Gault formula for creatinine clearance

- Hematology profile: complete blood count (CBC) with differential and platelet count
- Plasma HIV-1 RNA (Taqman v2.0)
 - Subjects who meet the criteria for virologic rebound should be managed according to Management of Suspected Virologic Failure (Section [6.7.1](#)).
- CD4+ T cell count
- Plasma storage sample for virology, safety and/or PK testing
- Serum and plasma storage samples for possible additional clinical testing (for subjects who provide consent)
- Serum pregnancy test (females of childbearing potential only).
 - Serum pregnancy testing may be performed more frequently if required by local regulations.
- Subject completed questionnaires:
 - SF-36 completed at Weeks 24, 48, 72, and 96 only
 - HIV-TSQs completed at Weeks 4, 24, 48, 72, and 96. HIV-TSQc (HIV Treatment Satisfaction Questionnaire Change) completed at Weeks 24, 48, 72, and 96.
 - VAS completed at all visits

The questionnaires should be completed by the subject. Subject is to read the questionnaire by him/herself and write/mark answers directly onto the questionnaire.

- Site-administered questions for Health Utilization Assessment to be completed
- Study drug dispensation (except at Week 2). Document study drug dispensation and accountability.
 - At Day 1, study drug will be dispensed for 30 days. At the Week 2 Visit, study drug will not be dispensed.

Note: At the Week 2 Visit, provide the scheduled Week 4 Visit date to the subject. Week 4 Visit should occur on day of hemodialysis. Instruct the subject to take study drug at Week 4 on-site (after completion of hemodialysis).

- Subjects should be instructed to take E/C/F/TAF FDC tablets once daily with food at the same time each day.
- Subjects should also be counseled regarding the importance of adherence and taking their study drugs at approximately the same time each day.

6.4. Treatment Assessments (Post Week 96 until the Open-Label Rollover Extension)

6.4.1. Post Week 96 Assessments to End of E/C/F/TAF visit

After the Week 96 visit, subjects will continue to take their study drug and attend visits every 12 weeks until the End of E/C/F/TAF visit. Study visits are to be completed within \pm 6 days of the protocol-specified visit date unless otherwise specified.

Note: Regularly scheduled evaluations will be made on all subjects whether or not they continue to receive study drug.

- Review of AEs and changes in concomitant medications
- Symptom-directed physical examination as needed
- Vital signs (blood pressure, pulse, respiration rate, and temperature) and weight
- Blood sample collection for the following laboratory analyses:
 - Chemistry profile: alkaline phosphatase, AST, ALT, GGT, total bilirubin, direct and indirect bilirubin, total protein, albumin, LDH, CPK, bicarbonate, BUN, calcium, chloride, creatinine, glucose, phosphorus, magnesium, potassium, sodium, uric acid, PT/INR, amylase (reflex lipase testing is performed in subjects with total amylase $> 1.5 \times$ ULN) and PTH
 - Metabolic assessments: Fasting (no food or drinks, except water, at least 8 hours prior to blood collection) glucose and lipid panel (total cholesterol, HDL, direct LDL, and triglycerides). If the subject has not fasted prior to the visit, the visit may proceed, but the subject must return within 72 hours in a fasted state to draw blood for the metabolic assessments (**Every 24 weeks**)
 - Estimated glomerular filtration rate according to the Cockcroft-Gault formula for creatinine clearance
 - Hematology profile: complete blood count (CBC) with differential and platelet count
 - Plasma HIV-1 RNA (Taqman v2.0)
 - Subjects who meet the criteria for virologic rebound should be managed according to Management of Suspected Virologic Failure (Section [6.7.1](#)).
 - CD4+ T cell count
 - Plasma storage sample for virology, safety and/or PK testing

- Serum and plasma storage samples for possible additional clinical testing (for subjects who provide consent)
- Serum pregnancy test (females of childbearing potential only).
 - Serum pregnancy testing may be performed more frequently if required by local regulations.
- Study drug dispensation. Document study drug dispensation and accountability.
- Subjects should be instructed to take E/C/F/TAF FDC tablets once daily with food at the same time each day. On the days of hemodialysis, subjects should be instructed to take study drug after completion of hemodialysis.

6.4.2. End of E/C/F/TAF Visit

At Week 96 or the End of E/C/F/TAF Visit, subjects will discontinue E/C/F/TAF FDC and have the option to receive OL B/F/TAF FDC.

Subjects who complete the study through the End of E/C/F/TAF Visit and do not continue on the open label B/F/TAF FDC extension phase will be required to return to the clinic after the End of E/C/F/TAF visit for a 30-Day Follow-Up Visit.

Subjects who have discontinued drug study prior to the Week 96 or End of E/C/F/TAF Visit will not be eligible for the open-label rollover extension; these subjects will be asked to continue attending the scheduled study visits through the Week 96 Visit.

The following will be performed at the End of E/C/F/TAF Visit:

- Review of AEs and changes in concomitant medications
- Symptom-directed physical examination as needed
- Vital signs (blood pressure, pulse, respiration rate, and temperature) and weight
- 12 Lead ECG (performed supine)
- Blood sample collection for the following laboratory analyses:
 - Chemistry profile: alkaline phosphatase, AST, ALT, GGT, total bilirubin, direct and indirect bilirubin, total protein, albumin, LDH, CPK, bicarbonate, BUN, calcium, chloride, creatinine, glucose, phosphorus, magnesium, potassium, sodium, uric acid, PT/INR, amylase (reflex lipase testing is performed in subjects with total amylase $> 1.5 \times \text{ULN}$) and PTH

Note: At the End of E/C/F/TAF Visit, analyses of glucose will be done as part of the fasting metabolic assessments and not as part of the chemistry profile.

- This sample should be drawn prior to hemodialysis.
 - The timing of draw and timing of hemodialysis should be recorded.

- Metabolic assessments: Fasting (no food or drinks, except water, at least 8 hours prior to blood collection) glucose and lipid panel (total cholesterol, HDL, direct LDL, and triglycerides). If the subject has not fasted prior to the visit, the visit may proceed, but the subject must return within 72 hours in a fasted state to draw blood for the metabolic assessments
- Estimated glomerular filtration rate according to the Cockcroft-Gault formula for creatinine clearance
- Hematology profile: complete blood count (CBC) with differential and platelet count
- Plasma HIV-1 RNA (Taqman v2.0)
- Subjects who meet the criteria for virologic rebound should be managed according to Management of Suspected Virologic Failure (Section [6.7.1](#)).
- CD4+ T cell count
- Plasma storage sample for virology, safety and/or PK testing
- Serum and plasma storage samples for possible additional clinical testing (for subjects who provide consent)
- Serum pregnancy test (females of childbearing potential only).
 - Serum pregnancy testing may be performed more frequently if required by local regulations.
- SF-36 and HIV-TSQs should be completed by the subject. Subject is to read the questionnaire by him/herself and write/mark answers directly onto the questionnaire.
- Study drug dispensation. Document study drug dispensation and accountability.
- Subjects who wish to continue in the Open-Label Rollover extension study will receive open label B/F/TAF FDC.

6.4.3. Open-Label Rollover Extension

For purposes of study visit identification during the open-label rollover extension, study visits will be identified by the number of weeks that have elapsed between the Week 96 or End of E/C/F/TAF Visit (whichever occurs later) and the corresponding open-label study visit, and labeled with “OL” (eg. Week 4 OL, Week 12 OL, Week 24 OL, etc.)

All subjects participating in the B/F/TAF OL extension phase will return for study visits at Week 4 OL, Week 12 OL and every 12 weeks thereafter for at least 48 weeks.

The Week 4 OL Visit should be completed within ± 2 days of the protocol-specified visit date. All other study visits are to be completed within ± 6 days of the protocol-specified visit date, unless otherwise specified.

The following will be performed at the Open-Label Extension Visits:

- Review of AEs and changes in concomitant medications
- Symptom-directed physical examination as needed (Complete physical exam performed at Week 48 OL)
- Vital signs (blood pressure, pulse, respiration rate, and temperature) and weight
- 12 Lead ECG (performed supine) (**Week 48 OL only**)
- Blood sample collection for the following laboratory analyses:
 - Chemistry profile: alkaline phosphatase, AST, ALT, GGT, total bilirubin, direct and indirect bilirubin, total protein, albumin, LDH, CPK, bicarbonate, BUN, calcium, chloride, creatinine, glucose, phosphorus, magnesium, potassium, sodium, uric acid, PT/INR, amylase (reflex lipase testing is performed in subjects with total amylase $> 1.5 \times$ ULN) and PTH.

Note: At Week 24 OL, and Week 48 OL analyses of glucose will be done as part of the fasting metabolic assessments and not as part of the chemistry profile.

- This sample should be drawn prior to hemodialysis.
 - The timing of draw and timing of hemodialysis should be recorded.
- Metabolic assessments: Fasting (no food or drinks, except water, at least 8 hours prior to blood collection) glucose and lipid panel (total cholesterol, HDL, direct LDL, and triglycerides). If the subject has not fasted prior to the visit, the visit may proceed, but the subject must return within 72 hours in a fasted state to draw blood for the metabolic assessments (Every 24 Weeks)
- Estimated glomerular filtration rate according to the Cockcroft-Gault formula for creatinine clearance
- Hematology profile: complete blood count (CBC) with differential and platelet count
- Plasma HIV-1 RNA (Taqman v2.0)
- Subjects who meet the criteria for virologic rebound should be managed according to Management of Suspected Virologic Failure (Section [6.7.1](#)).

- CD4+ T cell count
 - Plasma storage sample for virology, safety and/or PK testing
 - Serum and plasma storage samples for possible additional clinical testing (for subjects who provide consent)
 - Serum pregnancy test (females of childbearing potential only).
 - Serum pregnancy testing may be performed more frequently if required by local regulations.
 - At Week 4 OL, Week 24 OL and Week 48 OL study visits, on the day of hemodialysis, a sparse timed blood sample will be collected within 10 minutes before hemodialysis initiates from all subjects. Pre-dose (within 30 minutes prior to study drug administration) blood draws for plasma samples will also be collected at these visits. Study drug administration will be observed. Plasma concentrations of BIC may be determined. Plasma concentrations of other analytes may also be explored.
- SF-36 and HIV-TSQs should be completed by the subject. Subject is to read the questionnaire by him/herself and write/mark answers directly onto the questionnaire. **(Week 4 OL, Week 24 OL, and Week 48 OL only)**
 - Study drug dispensation. Document study drug dispensation and accountability.

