6.7.1. Management of Virologic Failure

- If the viral load is ≥ 50 copies/mL, HIV-1 RNA should be repeated at a scheduled or unscheduled visit (2-4 weeks after the date of the original test with HIV-1 RNA ≥ 50 copies/mL).
- Upon confirmation of HIV-1 RNA ≥ 50 copies/mL, potential causes of virologic failure should be documented. Assessments should include:
 - Adherence
 - Concomitant medication
 - Comorbidities (for example: active substance abuse, depression, other intercurrent illnesses)
- If virologic rebound is confirmed, and the HIV-1 RNA is < 400 copies/mL, subjects may remain on their current regimen at the discretion of the Investigator. Subject will return for a repeat within 2-4 weeks.

[figure not shown]
- If virologic failure is confirmed at the scheduled or unscheduled visit and HIV-1 RNA value is ≥ 400 copies/mL, the blood samples from the confirmation visit will be used for HIV-1 genotype/phenotype testing.
- If genotype/phenotype resistance to study drug is documented, study drugs should be discontinued.
- If no resistance is detected from genotype/phenotype testing, subject may remain on study drug and HIV-1 RNA should be repeated (2-4 weeks from the date of confirmed test with HIV-1 RNA ≥ 50 copies/mL). Investigators should carefully evaluate the benefits and risks of remaining on study drug for each individual subject and document this assessment in the subject's source documents. Investigators who opt to discontinue study drugs for an individual subject must discuss with the Medical Monitor prior to study drug discontinuation.

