6.7.3. Management of Virologic Rebound (Open-Label B/F/TAF Rollover Extension)

[figure not shown]
- If the viral load is ≥ 50 copies/mL, HIV-1 RNA should be repeated at a scheduled or unscheduled visit (2-3 weeks after the date of the original test with HIV-1 RNA ≥ 50 copies/mL).
- Upon confirmation of HIV-1 RNA ≥ 50 copies/mL, potential causes of virologic failure should be documented. Assessments should include:
 - Adherence
 - Concomitant medication
 - Comorbidities (for example: active substance abuse, depression, other intercurrent illnesses)
- If virologic rebound is confirmed, and the HIV-1 RNA is < 200 copies/mL, subjects may remain on their current regimen at the discretion of the Investigator. Subject will return for a repeat within 2-3 weeks.
- If virologic failure is confirmed at the scheduled or unscheduled visit and HIV-1 RNA value is ≥ 200 copies/mL, the blood samples from the confirmation visit will be used for HIV-1 genotype/phenotype testing.
- If genotype/phenotype resistance to study drug is documented, study drugs should be discontinued.
- If no resistance is detected from genotype/phenotype testing, subject may remain on study drug and HIV-1 RNA should be repeated (2-3 weeks from the date of confirmed test with HIV-1 RNA ≥ 50 copies/mL). Investigators should carefully evaluate the benefits and risks of remaining on study drug for each individual subject and document this assessment in the subject's source documents. Investigators who opt to discontinue study drugs for an individual subject must discuss with the Medical Monitor prior to study drug discontinuation.

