6.7.4. Subjects with ≥ 200 copies/mL of HIV-1 in the Absence of VR

Subjects with HIV-1 RNA < 50 copies/mL could subsequently experience unconfirmed blips of HIV-1 RNA ≥ 200 copies/mL. Such subjects will be analyzed for resistance if the unconfirmed rebound happens at the last visit while receiving study drugs (or within 72 hours of discontinuation of study treatment).

Please refer to [Figure 6-1](#) for the management of subjects who meet the criteria for virologic failure.

Figure 6-2. Virologic Rebound Schema (Open-Label B/F/TAF Rollover Extension)

- a If virologic rebound is not confirmed, the subject will remain on their current regimen.
- b If virologic rebound is confirmed and the HIV-1 RNA is ≥ 200 copies/mL, the HIV-1 genotype and phenotype (reverse transcriptase, protease and integrase) will be analyzed.
- c Based on the results of the genotypic and phenotypic assays, the subject will remain on study drugs or study drugs will be discontinued. If genotyping or phenotyping assays fail, a new ARV regimen may be configured at the discretion of the Investigator.
- d If no resistance is detected, HIV-1 RNA will be repeated (2-3 weeks later). Investigator reviews study drug continuation/discontinuation options and discuss with the Medical Monitor prior to study drug discontinuation
- e A new ARV regimen will be configured, at the Investigator's discretion, and the subject will remain in the study.

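### Protocol 6.4.3 sends virologic rebound on B/F/TAF to the E/C/F/TAF rule (resistance test at ≥ 400 copies/mL), although the extension's own rule tests at ≥ 200

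*Protocol*

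**What the plan says.** Protocol 6.4.3 lists the procedures at B/F/TAF extension visits. Under plasma HIV-1 RNA it says: "Subjects who meet the criteria for virologic rebound should be managed according to Management of Suspected Virologic Failure", and cites Section 6.7.1.

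Section 6.7.1 sets its resistance test as follows: "If virologic failure is confirmed at the scheduled or unscheduled visit and HIV-1 RNA value is ≥ 400 copies/mL", the confirmation sample goes for genotype/phenotype. For confirmed rebound below 400, "subjects may remain on their current regimen at the discretion of the Investigator. Subject will return for a repeat within 2-4 weeks". The accompanying schema, Figure 6-1, is labelled for E/C/F/TAF.

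Section 6.7.3 is titled for the B/F/TAF extension and uses a different threshold: "If virologic failure is confirmed at the scheduled or unscheduled visit and HIV-1 RNA value is ≥ 200 copies/mL". It also says: "If genotype/phenotype resistance to study drug is documented, study drugs should be discontinued". Figure 6-2, the extension schema, repeats the threshold in footnote b: "If virologic rebound is confirmed and the HIV-1 RNA is ≥ 200 copies/mL, the HIV-1 genotype and phenotype" are analysed. Protocol Appendix 3 (the extension procedures table), footnotes l and m, gives the 2-3 week retest and the 200 threshold and cites 6.7.3. SAP Appendix 2 does the same.

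Section 6.7.4 covers unconfirmed values of 200 or more in the extension: "Such subjects will be analyzed for resistance if the unconfirmed rebound happens at the last visit while receiving study drugs" or within 72 hours of stopping. It then refers the reader to Figure 6-1, not Figure 6-2, "for the management of subjects who meet the criteria for virologic failure". Section 6.5.2 covers early discontinuation in both phases and cites only 6.7.1.

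**The concern.** The section that tells a site what to do at an extension visit points to the rule for a different drug and phase. The two rules differ in the viral load that triggers resistance testing and in the time allowed for the confirmatory retest. Nothing in the protocol says which prevails.

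At stake is the management of a subject confirmed at 200-399 copies/mL on B/F/TAF. Under 6.7.1 that subject still has adherence, concomitant medication and comorbidities reviewed and a repeat viral load taken, but no resistance test. Without a test, the instruction to stop study drug on documented resistance cannot operate. Protocol 1.5 names loss of virologic control as a risk of taking part and offers clearly defined stopping parameters as mitigation. Two conflicting rules do not deliver that.

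There is also an internal oddity. With 6.4.3 as written, an unconfirmed value of 200 or more at the last on-drug visit is tested under 6.7.4, while a confirmed rebound at 200-399 earlier in the extension is not.

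**Working it through.** The plan gives no figure to reproduce. The check compares the two rules and works out the timing that follows.

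**The rules side by side**

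| | Rule cited by 6.4.3 (Section 6.7.1) | Rule written for the extension (Section 6.7.3) |
|---|---|---|
| Schema | Figure 6-1, E/C/F/TAF | Figure 6-2, B/F/TAF extension |
| Retest after first value ≥ 50 | 2-4 weeks (day 14-28) | 2-3 weeks (day 14-21) |
| Resistance test at confirmed value | ≥ 400 copies/mL | ≥ 200 copies/mL |
| Confirmed, below the test threshold | May stay on drug, repeat in 2-4 weeks | May stay on drug, repeat in 2-3 weeks |
| Resistance documented | Stop study drug | Stop study drug |
| Procedures-table footnotes l and m | Appendix 2 (E/C/F/TAF) | Appendix 3; SAP Appendix 2 |

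**Where testing differs, by confirmed value**

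- 50-199: neither rule tests.
- 200-399: 6.7.3 tests; 6.7.1 does not.
- 400 or more: both test.

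**Timing for a subject confirmed at 200-399.** Call the confirmation visit day C.

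- Under 6.7.3 the sample from day C is tested, so the delay is 0.
- Under 6.7.1 the repeat falls between C + 14 and C + 28 days (2 × 7 and 4 × 7). If that value is 400 or more, testing follows, 14-28 days later than under 6.7.3.
- If the value stays at 200-399, 6.7.1 leaves the rebound untested.

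**Confirmatory retest.** The latest permitted day is 28 under 6.7.1 and 21 under 6.7.3, a difference of 28 − 21 = 7 days.

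**Which rule is intended.** Section 6.7.3, Figure 6-2 footnote b, Section 6.7.4 and Appendix 3 all use 200 for this phase. Section 6.4.3 is the outlier. The same sentence citing 6.7.1 appears in the E/C/F/TAF visit sections (6.3, 6.4.1, 6.4.2), which suggests it was carried over.

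**Number affected.** Not calculable. The documents give neither the number of confirmed rebounds nor the viral-load distribution in the extension.

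**The case against.** The strongest reply is that this is a stale citation in an otherwise settled design. Section 6.7.3 carries the extension's name and sits close to 6.7.1. Appendix 3, the extension's own procedures table, directly instructs sites to use 6.7.3 and the 200 threshold. The title that 6.4.3 quotes for 6.7.1 is not even that section's exact heading. A site has to follow 6.4.3 and miss all of this before anyone is mishandled. The oddity with 6.7.4 likewise supposes a site that applies 6.7.4 but overlooks the section just before it.

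Much of that stands. The intent is clear, and this is an internal inconsistency rather than a questionable design decision. SAP Appendix 2 reproduces the protocol table, so it is not independent corroboration. But Appendix 3 contradicts 6.4.3 without taking precedence over it. Section 6 opens by directing readers to Appendix 2, whose footnotes give 400 and 2-4 weeks, and the wrong pointers in 6.7.4 and 6.5.2 add further routes to the E/C/F/TAF rule.

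Other limits also stand:

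- The 14-28 day delay assumes that a later value of 400 or more triggers testing under 6.7.1. That is a fair reading, but the section does not spell it out.
- The 7-day retest difference is an outer limit, because a retest on day 14-21 satisfies both rules.
- Section 6.5.3 allows discontinuation for lack of efficacy without a resistance result.
- On E/C/F/TAF at Week 48, 3.6% of 55 subjects (2 subjects) had HIV-1 RNA of 50 or more by snapshot. That is a different phase and measure, but it is consistent with few extension cases.

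**Conclusion.** The cross-reference in 6.4.3 is wrong as written and should be corrected. It is operative text that sets a clinical decision threshold, and followed literally it leaves confirmed rebound at 200-399 copies/mL on B/F/TAF without a resistance test. For such a subject the cost is a 14-28 day delay if the next value reaches 400, or no test if it does not, plus up to 7 extra days before the confirmatory retest.

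This rests on a site acting on 6.4.3 rather than on 6.7.3 or Appendix 3, and on at least one extension subject being confirmed in that range. Neither can be established from the documents. The effect is confined to individual subject management: the primary endpoint, the snapshot analysis and the sample size are unaffected, and the SAP plans no resistance analysis. The 6.7.4 pointer is a further slip of the same kind. The 6.5.2 citation matters little in practice, because 6.7.4 already tests an unconfirmed value of 200 or more at or within 72 hours of discontinuation, and study drug has by then stopped.

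**What to change.** Correct three cross-references by clarification letter or site memo:

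- 6.4.3: cite 6.7.3 instead of 6.7.1.
- 6.7.4: cite Figure 6-2 instead of Figure 6-1.
- 6.5.2: add 6.7.3/6.7.4 for extension subjects.

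A look-back is the more useful step, because SAP Section 9 describes at least the predose extension draws as already collected. Search the individual extension HIV-1 RNA values for any subject confirmed at 200-399 copies/mL and check whether genotype/phenotype was done. The by-visit categories in SAP 7.2.2.1 stop at 50 copies/mL and above, so the planned tables would not show these subjects. If any subjects are still being followed, repeat the search once follow-up ends.

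Where a test was missed, run it on stored plasma if available. Section 6.4.3 lists a storage sample for virology at extension visits, but a confirmation taken at an unscheduled visit may have none.

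The cost is the three text corrections, one data query and, at most, resistance assays for a few subjects. No SAP change, new visits or new samples are needed.
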